7.5 Adjustments for Multiple Comparisons

Secondary endpoints will be tested only if the primary efficacy endpoint is significant. Secondary endpoints will be tested in a hierarchical fashion to preserve alpha. Each secondary endpoint will be tested at alpha 0.05, but testing will stop when any secondary endpoint fails to achieve significance.

Secondary Endpoints #1, 2 and 8 are not truly independent secondary endpoints; rather they are secondary analyses of the primary efficacy endpoint. To maintain the hierarchical approach for testing the hypotheses and for consistency with the Clinical Investigational Plan, these secondary analyses of the primary endpoint are considered secondary endpoints in this section.

7.6 Demographic and Other Baseline Characteristics

Subject demographics and baseline characteristics; including epilepsy diagnosis, seizure frequency, and other medical history; will be summarized using descriptive statistics for each of the analysis populations.

7.8 Interim Analyses

No formal interim analysis is planned. Any unplanned interim analyses will be conducted under the auspices of the data monitoring committee (DMC) assigned to this study. The DMC is authorized to review interim efficacy and safety analyses and, if necessary, to ensure patient safety, to release results on an as-needed basis to the Medtronic SLATE study team and participating investigators. The DMC will make a recommendation to continue, modify, suspend, or discontinue the study if necessary, to ensure

SLATE Statistical Analysis Plan Revision 1.0 Page 11 of 23 Medtronic

patient safety. Any such release will be documented and described in the final study report. Study sites will not receive interim results unless they need to know for the safety of their patients.

7.9 Evaluation of Objectives

7.9.1 Primary Safety Endpoint

The primary safety endpoint is the incidence of qualifying device-, procedure-, or anesthesia-related adverse events (defined in Appendix 2) through 12 months following the Visualase procedure.

7.9.1.1 Hypotheses

It is hypothesized that the upper bound of the 95% CI for the proportion of subjects experiencing any qualifying device-, procedure-, or anesthesia-related adverse events (per Appendix 2) through 12 months following the Visualase procedure will be less than 40%. The hypotheses associated with this endpoint are as follows:

Null Hypothesis: $\pi V \ge 0.4$

Alternate Hypothesis: $\pi V < 0.4$

Where πV is the proportion of subjects treated with Visualase experiencing any qualifying AE.

7.9.1.2 Performance Requirements

The criteria of an AE rate of 40% is based on the analysis by Attiah *et al.* (2014). Refer to CIP Section 3.2 for details.

7.9.1.3 Analysis Methods

An exact 95% CI (Clopper 1934) will be calculated to determine if the upper bound of the CI for qualified AEs is less than 40%.

7.9.2 Primary Efficacy Endpoint

The primary efficacy endpoint is seizure freedom (defined as Engel Class I, Appendix 1) at 12 months following the Visualase procedure (starting at 30 days post-procedure through 365 days post-procedure, to align with Engel Class I definition).

7.9.2.1 Hypotheses

It is hypothesized that the lower bound of the 95% CI for seizure freedom at 12 months following the Visualase procedure will be greater than 43%. The hypotheses associated with this endpoint are as follows:

Revision 1.0 Page 12 of 23

Null Hypothesis: $\pi V \le 0.43$

Alternate Hypothesis: $\pi V > 0.43$

Where πV is the proportion of subjects treated with Visualase experiencing no seizures.

An exact 95% CI will be calculated to determine if the lower bound of the CI for seizure freedom at 12 months following the Visualase procedure (π V) will be greater than 43%.

7.9.2.2 Performance Requirements

The performance criterion of seizure-free percentage > 43% is based on the analysis by Attiah *et al.* (2014). Refer to CIP section 3.2 for details.

7.9.2.3 Analysis Methods

An exact 95% CI for the percentage of subjects who are seizure free will be calculated.

7.9.3 Secondary Endpoints

All secondary endpoints have specific hypotheses to be tested. The hypotheses associated with each of these secondary endpoints will be tested in a hierarchical fashion. If the primary efficacy endpoint is not significant, then no secondary endpoints will be tested. Testing of these secondary endpoints will proceed in the following order using an alpha of 0.05 and will stop if any test fails to reach significance.

7.9.3.1 Secondary Endpoint #1

Seizure freedom (defined as Engel Class I, Appendix 1) at 12 months following the Visualase procedure compared to historical reference threshold for continued medical therapy

It is hypothesized that the seizure freedom at 12 months following the Visualase procedure will be superior to 8% reported in the literature for continued medical therapy (Wiebe 2001). The hypotheses associated with this endpoint are as follows:

Null Hypothesis: $\pi V \le 8\%$ Alternate Hypothesis: $\pi V > 8\%$

Where πV is the proportion of subjects treated with Visualase experiencing no seizures.

An exact 95% CI for the percentage of subjects who are seizure free will be calculated.

7.9.3.2 Secondary Endpoint #2

Seizure freedom (defined as Engel Class I, Appendix 1) at 12 months following the Visualase procedure, including subjects who are retreated with Visualase

Revision 1.0 Page 13 of 23

It is hypothesized that the lower bound of the 95% CI for seizure freedom at 12 months following the Visualase procedure, including subjects retreated with Visualase, will be greater than 43%. Subjects retreated with Visualase will count toward the secondary efficacy endpoint based on their outcome after retreatment. If they have become seizure free and have reached 12 months follow-up from time of retreatment, they are counted as seizure free. Otherwise, they will count as not seizure free. The hypotheses associated with this endpoint are as follows:

Null Hypothesis: $\pi V \le 0.43$ Alternate Hypothesis: $\pi V > 0.43$

Where πV is the proportion of subjects treated with Visualase experiencing no seizures.

An exact 95% CI will be calculated to determine if the lower bound of the CI for seizure freedom at 12 months (π V) following a subject's last Visualase procedure, including patients retreated with Visualase, will be greater than 43%.

7.9.3.3 Secondary Endpoint #3

Within-subject change of Boston Naming Test score (English language version), from baseline to 12 months following the Visualase procedure

It is hypothesized that the Boston Naming Test score will not decrease from baseline to 12 months following the Visualase procedure. The hypotheses associated with this endpoint are as follows:

Null Hypothesis: μ (V-BNT - BSL-BNT) + $\delta \le 0$ Alternate Hypothesis: μ (V-BNT - BSL-BNT) + $\delta > 0$

Where μ (V-BNT - BSL-BNT) = mean difference in the Boston Naming Test score from baseline to Month 12 post Visualase.

A non-inferiority test will be performed using a paired t-test, with a non-inferiority delta (δ) of one Reliable Change Index (RCI) of 5 points, to test the hypothesis of no reduction. The 5-point RCI is based on published literature (Sawrie 1996). A two-tailed alpha of 0.05 will be used.

7.9.3.4 Secondary Endpoint #4

Within-subject change of Rey Auditory Verbal Learning Test 5-Trial Total score (English language version), from baseline to 12 months following the Visualase procedure

It is hypothesized that the Rey Auditory Verbal Learning Test 5-Trial Total score will not decrease from baseline to 12 months following the Visualase procedure. The hypotheses associated with this endpoint are as follows:

Null Hypothesis: μ (V-RAVLT - BSL-RAVLT) + $\delta \le 0$ Alternate Hypothesis: μ (V-RAVLT - BSL-RAVLT) + $\delta > 0$

Revision 1.0 Page 14 of 23

Where μ (V-RAVLT - BSL-RAVLT) = mean difference in the Rey Auditory Verbal Learning Test 5-Trial Total score from baseline to Month 12 post Visualase.

A non-inferiority test will be performed using a paired t-test, with a non-inferiority delta (δ) of one Reliable Change Index (RCI) of 15 points, to test the hypothesis of no reduction. The 15-point RCI is based on published literature (Sawrie 1996). A two-tailed alpha of 0.05 will be used.

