This study employs a rigorous battery of neuropsychological tests to better characterize individual change in naming and memory following laser ablation. Changes in these cognitive scores are expected and consequently are not considered as adverse events unless the magnitude of change exceeds expectations by the site investigator.

Similarly, adverse events related to depression and anxiety will also be based on site investigator assessment, and a decline in mood assessment scores alone will not be considered an adverse event.

For AEs that require immediate reporting (see Table 9), initial reporting may be done by completing as much information as possible on an AE eCRF. The remainder of the AE eCRF must be completed as soon as possible.

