7.2 General Statistical Methods

Statistical analyses will be performed using SAS Software, Version 9.4 or later. Continuous variables will be summarized by N, mean, standard deviation, median, quartile1 and quartile3, minimum, and maximum. Categorical variables will be described by number and percentage. For binary endpoints, a 95% exact CI will be provided.

All statistical tests will be conducted at a two-sided alpha level of 0.05, unless otherwise stated.

This SAP includes a comprehensive description of the statistical methods and reports to be included in the final study report.

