7.4 Handling of Missing, Unused, and Spurious Data and Dropouts

7.4.1 Missing Data

Missing primary efficacy endpoint values and missing secondary endpoint values associated with testable hypotheses will be imputed for analysis with the mITT analysis population. Missing primary efficacy endpoint data will be imputed as a binary outcome of seizure freedom, regardless of missing pattern. No daily level imputation will be conducted.

The primary method of imputation will be multiple imputation (SAS PROC MI followed by MIANALIZE). Ten repetitions will be performed and, if needed, will be increased until the algorithm converges.

The Markov chain Monte Carlo (MCMC) method or Fully Conditional Specification (FCS) will be used with the default number of burn-in iterations before the imputation. The model variables will include: age, sex, race (white, African American, or other), and duration of disease.

SLATE Statistical Analysis Plan		Form
Revision 1.0	Page 10 of 23	Medtronic

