7.9.3.5 Secondary Endpoint #5

Within-subject change of the Quality of Life in Epilepsy inventory (QOLIE-31) score (English language version), from baseline to 12 months following the Visualase procedure, categorized as -1 if the decrease is clinically significant (\leq -11.8), categorized as 0 if not clinically significant (-11.7 to +11.7), and categorized as +1 if the increase is clinically significant (\geq 11.8).

It is hypothesized that the QOLIE-31 score will increase (improve) from baseline to 12 months following the Visualase procedure. The hypotheses associated with this endpoint are as follows:

Null Hypothesis: M (V-QOLIE-31 - BSL-QOLIE-31) \leq 0 Alternate Hypothesis: M (V-QOLIE-31 - BSL-QOLIE-31) > 0

Where M (V-QOLIE-31 - BSL-QOLIE-31) = sign-test statistic ([increases-decreases]/2) in the Quality of Life in Epilepsy inventory from baseline to Month 12 post Visualase.

A sign test will be used to determine if the median categorical change is significantly greater than zero. The Minimally Clinically Important Difference (MCID) of 11.8 points for the QOLIE-31 is based on published literature (Wiebe 2002).

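### Secondary endpoints 3 and 4 are worded as no decrease in naming and verbal memory, but a pass shows only that the mean loss is below 5 or 15 points

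*SAP*

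**What the plan says.** SAP 7.9.3.3 states for the Boston Naming Test (BNT): "It is hypothesized that the Boston Naming Test score will not decrease from baseline to 12 months". SAP 7.9.3.4 states for the Rey Auditory Verbal Learning Test (RAVLT): "It is hypothesized that the Rey Auditory Verbal Learning Test 5-Trial Total score will not decrease from baseline".

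Both sections then print the formal hypotheses. The alternative is that mean change plus δ exceeds zero. The test is a paired t-test for non-inferiority at two-tailed alpha 0.05. For BNT the margin is "of one Reliable Change Index (RCI) of 5 points, to test the hypothesis of no reduction"; for RAVLT it is "of one Reliable Change Index (RCI) of 15 points, to test the hypothesis of no reduction". Protocol 14.6.3 and 14.6.4 use the same wording and margins.

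Three other places bear on what a reader of the results would see:

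- SAP 7.2 sets general summaries: "Continuous variables will be summarized by N, mean, standard deviation, median, quartile1 and quartile3, minimum, and maximum". It does not name change scores.
- Protocol 10.2.1 says the cognitive battery is meant to describe individual change, and that changes in these scores are "not considered as adverse events unless the magnitude of change exceeds expectations by the site investigator".
- For QOLIE-31, SAP 7.9.3.5 classifies each subject's change, for example "categorized as -1 if the decrease is clinically significant". SAP 7.9.3.6 and 7.9.3.7 do likewise for the SF-36 scores. No visible text does this for BNT or RAVLT.

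**The concern.** The hypothesis in words and the hypothesis in symbols differ. In words, the score does not fall. In symbols, the mean may fall by anything short of 5 or 15 points. On the scales described in Protocol 7.5.6, 5 points is 8.3% of the 60 BNT items, and 15 points is 20% of the RAVLT five-trial maximum (15 words × 5 trials = 75).

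If the report takes its conclusion from the wording, a pass would be described as no reduction in naming or verbal memory, and the same data could show a statistically clear reduction. Protocol 3.2 presents the lack of cognitive deficit as a distinguishing feature of the device, so readers will care about the exact claim.

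The margin is also one Reliable Change Index (RCI), which in general use is a yardstick for one person's change. Applied to a group mean, it leaves open how many subjects individually lost that much.

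**Working it through.** **Inputs from the documents.** Margins are 5 (BNT) and 15 (RAVLT). The test is a paired t-test at two-tailed 0.05, so 0.025 in the tested direction. SAP 6 gives N=109 evaluable before the English-language restriction and N=55 if half of those are used.

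**Assumed.** Every SD of change, normality unless stated, and complete data. The planned test would also use imputed values, because "missing secondary endpoint values associated with testable hypotheses will be imputed for analysis with the mITT analysis population".

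**The plan's own figures.** 0.73 × 150 = 109.5 and 0.5 × 109 = 54.5, in line with 109 and 55. The 86% power in SAP 6 cannot be reproduced, because no effect size or SD is visible. Solved backwards, it needs a standardized effect of 0.417 at N=55 (two-sided 0.05). It is described as power to detect a change, so it may not refer to these tests. Nothing below depends on it.

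**Step 1: largest mean loss that still passes.** The test passes when the lower 95% limit of mean change is above -margin, so the limit is

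margin - t(0.975, N-1) × SD / √N.

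At N=55, t = 2.005 and √55 = 7.416, so the multiplier is 0.2703.

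| Test | Assumed SD | Largest passing mean loss | 95% CI of mean change there |
|---|---|---|---|
| BNT | 5 | 5 - 1.35 = 3.65 | -5.00 to -2.30 |
| BNT | 10 | 5 - 2.70 = 2.30 | -5.00 to +0.41 |
| RAVLT | 10 | 15 - 2.70 = 12.30 | -15.00 to -9.59 |
| RAVLT | 15 | 15 - 4.06 = 10.94 | -15.00 to -6.89 |

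The upper limit is -margin + 2 × 0.2703 × SD. It lies below zero when SD < margin / 0.5407, that is, below about 9.2 (BNT) or 27.7 (RAVLT). For SDs under those values, the test can pass while the same data show a significant fall.

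**Step 2: share of subjects losing at least the margin, at that limit.** With normal changes the SD cancels: share = Φ(-t/√N). At N=55, Φ(-0.2703) = 39.3%. At N=109, Φ(-0.1899) = 42.5%, but that N is the sample before the English-language restriction.

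**Step 3: away from the limit.** Chance of passing (noncentral t) when the stated share of the population shows an observed loss of at least the margin:

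| Share | N=55 | N=109 (before restriction) |
|---|---|---|
| 25% | 99.8% | >99.9% |
| 30% | 96.8% | >99.9% |
| 35% | 80.1% | 97.9% |

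In the 30% case at N=55, 40,000 simulated trials put the 95% CI wholly below zero in 93% of passing trials (if RCI = 1.0 SD) to 100% (if RCI = 1.96 SD).

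**Step 4: noise.** These are observed changes. With no true change, Φ(-RCI/SD) of subjects would still fall at or below -RCI: 16% at RCI = 1.0 SD and 2.5% at 1.96 SD. In the 30% case the excess over chance is therefore about 14 to 28 percentage points.

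**Step 5: non-normal check.** Assume 40% of subjects lose 1.5 RCI on average (SD 0.25 RCI) and 60% are stable (SD 0.4 RCI). Then 39.5% are observed at or below -RCI, and the test passes about 95% of the time at N=55.

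**The case against.** The strongest reply is that the plan hides nothing. Each worded hypothesis is followed by symbols containing δ and by a sentence that names a non-inferiority test and its margin. That stands. A reader might infer a concealed margin or a wrong formula; the documents show neither, and the decision rule is clear.

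A second reply is that a decline would be seen anyway. If SAP 7.2 is applied to change scores, N, mean and SD give the confidence interval, and under normality they estimate the share of decliners well. Quartiles help too. Taking Q1 at N=55 as the 14th ordered value, it falls at or below -RCI in about 80% of passing trials in the 30% case, and in about 99% in the mixture case. Much of this stands. It weakens any claim that individual decline would be invisible. It does not correct the worded conclusion, and the summaries give no count with an interval. Adverse event reporting is only a partial route, because it rests on the investigator's expectations.

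A third reply is that a table of decliners may already be planned. A reader might infer from the visible text that there is none. The documents do not support that: Protocol 14.7 and SAP 7.1.2, 7.4.2 and 7.7 are not visible, and text is missing around SAP pages 16-17 and 20-22.

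Finally, the documents do not define the RCI, and whether 5 and 15 points are good cut-offs for an individual cannot be checked here. The arithmetic needs only the point values.

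**Conclusion.** The concern holds as a mismatch between words and test. A pass on endpoint 3 or 4 supports a mean loss below 5 or 15 points and nothing stronger. At N=55 it can occur with a mean change significantly below zero, for SDs of change under about 9.2 (BNT) or 27.7 (RAVLT).

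The 39% share is the boundary case. It assumes normal changes and includes measurement noise, so it should not be read as 39% of subjects truly harmed or as an expected result. The pass probabilities also ignore imputation.

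Severity is minor: only two secondary endpoints are affected and no decision rule changes.

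**What to change.** - **Wording.** In SAP 7.9.3.3 and 7.9.3.4, replace the no-decrease and no-reduction wording with: the mean decrease from baseline to 12 months is smaller than 5 points (BNT) / 15 points (RAVLT). State that this is the only conclusion allowed on a pass, and report the mean change with its 95% CI. Make the same change in Protocol 14.6.3 and 14.6.4, or record it as a clarification under SAP 7.11, which now says nothing differs from the protocol.
- **Count of decliners.** Beside each test, report the number and percentage of English-version subjects with both scores whose score fell by at least 5 / 15 points, without imputation, with an exact 95% CI and the number missing. For example, 16 of 55 is 29%, CI 18% to 43%. Note that some declines arise by chance and that a single arm has no reference for practice effects. If text not visible here already plans such a table, link it to these endpoints.

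The table is descriptive. Margin, alpha, imputation for the mean test and testing order stay unchanged. The cost is a few sentences and one table from scores already collected. Protocol 14.2 asks for an amendment only when a principal feature changes, and the test does not change. The downside is a more modest claim.

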7.9.3.5 Secondary Endpoint #5

Within-subject change of the Quality of Life in Epilepsy inventory (QOLIE-31) score (English language version), from baseline to 12 months following the Visualase procedure, categorized as -1 if the decrease is clinically significant (\leq -11.8), categorized as 0 if not clinically significant (-11.7 to +11.7), and categorized as +1 if the increase is clinically significant (\geq 11.8).

It is hypothesized that the QOLIE-31 score will increase (improve) from baseline to 12 months following the Visualase procedure. The hypotheses associated with this endpoint are as follows:

Null Hypothesis: M (V-QOLIE-31 - BSL-QOLIE-31) \leq 0 Alternate Hypothesis: M (V-QOLIE-31 - BSL-QOLIE-31) > 0

Where M (V-QOLIE-31 - BSL-QOLIE-31) = sign-test statistic ([increases-decreases]/2) in the Quality of Life in Epilepsy inventory from baseline to Month 12 post Visualase.

A sign test will be used to determine if the median categorical change is significantly greater than zero. The Minimally Clinically Important Difference (MCID) of 11.8 points for the QOLIE-31 is based on published literature (Wiebe 2002).

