7.9.3.6 Secondary Endpoint #6

Within-subject change of SF-36 quality of life questionnaire Mental Component Score (English language version), from baseline to 12 months following the Visualase procedure, categorized as -1 if the decrease is clinically significant (\leq -4.58), categorized as 0 if not clinically significant (-4.57 to +4.57), and categorized as +1 if the increase is clinically significant (\geq 4.58).

It is hypothesized that the SF-36 Mental Component Score (MCS) will increase (improve) from baseline to 12 months following the Visualase procedure. The hypotheses associated with this endpoint are as follows:

Null Hypothesis: M (V-SF-36 - BSL-SF-36-MCS) \leq 0 Alternate Hypothesis: M (V-SF-36 - BSL-SF-36-MCS) > 0

Where M (V- SF-36-MCS - BSL- SF-36-MCS) = sign-test statistic ([increases-decreases]/2) in the SF-36 quality of life questionnaire MCS from baseline to Month 12 post Visualase.

Revision 1.0 Page 15 of 23

A sign test will be used to determine if the median categorical change is significantly greater than zero. The MCID of 4.58 points for the SF-36-MCS is based on published literature (Wiebe 2002).

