7.9.3.7 Secondary Endpoint #7

Within-subject change of SF-36 quality of life questionnaire Physical Component Score (English language version), from baseline to 12 months following the Visualase procedure, categorized as -1 if the decrease is clinically significant (\leq -3.02), categorized as 0 if not clinically significant (-3.01 to +3.01), and categorized as +1 if the increase is clinically significant (\geq 3.02).

It is hypothesized that the SF-36 Physical Component Score (PCS) will increase (improve) from baseline to 12 months following the Visualase procedure. The hypotheses associated with this endpoint are as follows:

Null Hypothesis: $M (V-SF-36-PCS - BSL-SF-36-PCS) \le 0$ Alternate Hypothesis: M (V-SF-36-PCS - BSL-SF-36-PCS) > 0

Where M (V-SF-36-PCS - BSL- SF-36-PCS) = sign-test statistic ([increases-decreases]/2) in the SF-36 quality of life questionnaire PCS from baseline to Month 12 post Visualase.

A sign test will be used to determine if the median categorical change is significantly greater than zero. The MCID of 3.02 points for the SF-36 Physical Component Score is based on published literature (Wiebe 2002).

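### Secondary endpoints 5–7: the sign test shows that more subjects improve than worsen by the MCID, not that the median category exceeds zero

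*SAP*

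**What the plan says.** SAP 7.9.3.5 codes the QOLIE-31 change from baseline to 12 months at an MCID of 11.8 points. A subject is +1 for a gain of at least that size, −1 for a loss of at least that size, and otherwise "categorized as 0 if not clinically significant (-11.7 to +11.7"). SAP 7.9.3.6 and 7.9.3.7 do the same for the SF-36 mental and physical component scores, with zero bands of ±4.57 and ±3.01 points.

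M is defined for endpoint 5 as the "sign-test statistic ([increases-decreases]/2) in the Quality of Life in Epilepsy inventory from baseline to Month 12 post Visualase", and the hypotheses are written on it: "Alternate Hypothesis: M (V-QOLIE-31 - BSL-QOLIE-31) > 0". The purpose of the test is then given as: "A sign test will be used to determine if the median categorical change is significantly greater than zero". Endpoints 6 and 7 carry the same sentence, and protocol 14.6.5–14.6.7 matches.

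SAP 7.2 sets the level: "All statistical tests will be conducted at a two-sided alpha level of 0.05, unless otherwise stated". Neither document states another rule for zeros, a minimum proportion of improvers, or an expected split between the three categories.

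**The concern.** For a continuous change with no ties, a sign test and a test of the median are the same thing. Here the plan deliberately creates a tie category, everyone whose change is smaller than the MCID, and the two questions separate. The statistic compares +1 with −1. The stated purpose concerns the middle subject when all subjects are ranked.

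The formal hypotheses do not settle which is meant, because M is computed from the sample and is not a population quantity. The only population target named is the median category, and the test does not address it.

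At stake is what endpoints 5–7 can be said to show. They are formal hypotheses in the fixed sequence. A sponsor who took the plan at its word could describe a significant result as a median change above zero while its own table showed a median of exactly zero.

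**Working it through.** **Plan's own figure.** No power or sample size is given for these three tests. The nearest figure, 86% power at N = 55 (SAP section 6), concerns the neuropsychological assessments. Its effect size is not stated, so it cannot be reproduced and does not bear on the sign tests.

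**Inputs.** Coding and M from SAP 7.9.3.5–7.9.3.7; two-sided alpha 0.05 from SAP 7.2; N = 55 and N = 109 from SAP section 6. N = 90 is an illustration: 60% of 150 treated subjects, if Spanish-language subjects reach the 40% cap and attrition is the same in both language groups.

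**What the test examines.** Let u be the number at +1, d the number at −1, and m = u + d. Then M = (u − d)/2, and the exact two-sided p-value when u > d is

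p = 2 × Σ (k = u to m) C(m, k) / 2^m.

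The number of zeros appears in neither expression. Rejection in favour of improvement supports P(+1) > P(−1). That zeros drop out is inferred from M and is the usual sign test; the SAP does not say so in words.

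**What the median claim needs.** On a −1/0/+1 scale the population median exceeds zero only if P(+1) > 0.5, with every subject in the denominator. The exact two-sided test needs the smallest r with 2 × P(Bin(N, 0.5) ≥ r) ≤ 0.05:

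| N | +1 subjects needed |
|---|---|
| 55 | 36 (65.5%) |
| 90 | 55 (61.1%) |
| 109 | 66 (60.6%) |

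**Significant results with a sample median of 0.**

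| Improved | Worsened | Unchanged | N | Two-sided p |
|---|---|---|---|---|
| 30 | 10 | 50 | 90 | 0.002 |
| 20 | 7 | 28 | 55 | 0.019 |
| 8 | 1 | 46 | 55 | 0.039 |
| 6 | 0 | 49 | 55 | 2 × (1/2)^6 = 0.031 |

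In the first row, ranks 11 to 60 of 90 are all 0, so the middle two (45 and 46) are 0. Only 30 subjects improved, where the median claim would need 55. The last row is the smallest possible win: 5 against 0 gives 2 × (1/2)^5 = 0.0625.

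**How often this would happen.** The documents give no expected split, so these are assumptions. The true median is 0 in every row.

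| Improved / worse / unchanged | Sign test rejects, N = 55 | N = 109 | Median test rejects, either N |
|---|---|---|---|
| 20% / 5% / 75% | 0.53 | 0.87 | about 0 |
| 40% / 10% / 50% | 0.88 | 0.996 | 0.0001 or less |

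A simulation with an assumed normal QOLIE-31 change (mean 6, SD 16, n = 55) points the same way. The sign test rejects in 61% of trials, and in 59% of trials it rejects with half or fewer of the subjects improved.

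**The case against.** The strongest reply is that the test itself is sound. M > 0 says that improvers outnumber worseners, the obvious reading of a sign test, and counting only MCID-sized changes is a legitimate choice. The decision rule, alpha and p-value would be the same after any rewording. With no true change (assumed SD 16, MCID 11.8), the simulated rate of false rejection in favour of improvement was 0.015 at n = 55 and 0.018 at n = 90, below 0.025. SAP 7.2 already calls for counts and percentages of categorical variables, so a median of zero would be visible beside the p-value. All of this stands. It does not rescue the stated purpose, which the test cannot serve.

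The same reply disposes of several stronger readings that a reader might infer:

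- *The test is routinely won with almost nobody changed.* The 6-against-0 case is an extreme, and each worsening raises the number of improvements needed. Under mean 6, SD 16, about 51% fall in the zero band, and none of 40,000 simulated trials rejected with 80% or more unchanged.
- *The test is too weak and should become a t-test or Wilcoxon test.* The documents give no means or SDs for these endpoints, so any power comparison rests on assumptions. A test of mean change also answers a different question.
- *The wording blocks later endpoints.* Stopping after a failure at endpoint 5 is the intended fixed sequence.
- *The report will make the false statement.* Neither document prescribes the report's wording; the plan only invites it.

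**Conclusion.** The stated target is wrong as written for endpoints 5, 6 and 7 in both documents. The planned test supports the claim that more subjects improve than worsen by at least the MCID. It does not support a claim about the median category, which would need at least 36 of 55 or 66 of 109 subjects at +1.

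This conclusion follows from the definition of M and from arithmetic, given the usual handling of zeros that M implies. It does not depend on the assumed splits, means or SDs, which only indicate that a significant result with a median of zero would be common under plausible conditions. Type I error for the narrower question is not inflated, and no change of test is needed. The fault lies in the hypothesis and in the conclusion drawn from it.

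**What to change.** Keep the sign test. In SAP 7.9.3.5–7.9.3.7 and protocol 14.6.5–14.6.7:

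1. Restate the hypotheses as H0: P(improve by MCID or more) ≤ P(worsen by MCID or more), against H1: P(improve) > P(worsen).
2. Delete the claim about the median category, and say in words that subjects coded 0 do not enter the test.
3. Report the percentages improved, unchanged and worsened among all analysed subjects, with the net difference (improved minus worsened) and its 95% CI, and name the interval method.

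As an illustration with 30, 50 and 10 of 90: the net difference is (30 − 10)/90 = 22.2 percentage points. The large-sample standard error is √[(0.4444 − 0.2222²)/90] = 0.0663, giving a 95% CI of 22.2 ± 1.96 × 6.63, or about 9.2 to 35.2 points. A method suited to small counts would be preferable if few subjects leave the zero band.

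The cost is wording plus one interval per endpoint, with no change to data collection, sample size, test or testing order. SAP 7.11, which now records no changes from the protocol, should list the restatement. Protocol 14.2 requires an amendment only where a principal feature changes; other changes go in the clinical study report with their justification. The price to the sponsor is a slightly less favourable claim.
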